# 7.4 Eligibility criteria for continued treatment in the extension period

Criteria for the transition to the extension period (V6/6a) and for continued treatment within the extension period (V10/10a and V14/14a) are listed below. (Note that the pairs of visits 6/6a, 10/10a and 14/14a will normally take place on the same respective day.)

If these eligibility criteria are not fulfilled at the end-of-cycle visit postponement of study treatment may take place at the beginning of the following injection cycle of the extension period. The re-injection visit can be postponed for up to a maximum of two weeks (but no longer than 18 weeks after the preceding treatment visit). For subjects who still do not fulfill the eligibility criteria at the revisit, study participation will be ended.

	Eligibility Criteria for Extension Treatment	Ratio- nale	Visits 6, 6a, 10, 10a, 14, 14a
1.	Clinical need for re-injection.	Ind	Х
2.	Absence of medically-relevant severe adverse events of special interest that are judged to have a causal relationship to the study treatment (indicative of toxin spread in the area of injection), especially respiratory arrest/distress/failure and dysphagia necessitating diet changes occurred during any period of the study.	Safety	Х
3.	No concomitant infection or inflammation in the head and neck region.	Safety	Х

Page 52 of 183

		Eligibility Criteria for Extension Treatment	Ratio- nale	Visits 6, 6a, 10, 10a, 14, 14a
4.	Neg fem	ative result of pregnancy test (testing only performed for ale with history of menarche, i.e. the first menstrual bleeding).	Safety	Х
5.	No :	significant risk of suicidality since last injection based on the Investigator's judgment, and	Safety	Х
	•	if appropriate, as indicated by a response of "no" to questions 4 or 5 in the suicidal ideation section of the C-SSRS		
	•	and no non suicidal self-injurious behavior		
	•	and no suicidal behavior.		

Definition of indication for continued study treatment [Ind]; administrative [Adm].

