### **10.7** Other safety assessments

A dental and oral examination will be performed by a qualified dental health provider (minimum qualification: dentist) at screening (V1), V3 and V6 of the main study period, at V10 and at the-end-of-study visit (V18), or at the subject's last study visit if this is earlier. Results of dental and oral examination will be reported in terms of adverse events: findings indicating a worsening of the subject's condition since screening are to be recorded as adverse events.

Details are given in Appendices 16.4.1.

As part of the physical examination, particular attention will be paid to lungs in order to detect any signs of aspiration, at baseline and every subsequent visit.

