#### 6.5.3 Other safety variables

- Occurrence of non-treatment emergent AEs.
- Occurrence of non-serious TEAEs per period.
- Occurrence of TEAEs by worst intensity per period and injection cycle.
- Occurrence of TEAEs by worst causal relationship per period and injection cycle.

- Occurrence of related serious TEAEs per period and injection cycle.
- Occurrence of TEAEs by worst outcome per period and injection cycle.
- Listing of all serious TEAEs of subjects who died per period.
- Listing of TEAEs of standard MedDRA query suicide/self-injury and of TEAEs with possibly suicidal events, per period.
- Vital signs (blood pressure, heart rate, body temperature) at study baseline, V3 (week 4), V6 (week 16), during the main period, at injection visits in the extension period, at end of cycle visits in the extension period and at the end-of-study visit (V18) (Week 64).
- Body height and body mass index (BMI), calculated from body weight and height, at study baseline, final visit of the main period (V6) (Week 16), and end-of-study visit (V18) (Week 64).
- Body weight at study baseline, final visit of the main period (V6) (Week 16), at injection visits in the extension period, at end-of cycle visits in the extension period and end-of-study visit (V18) (Week 64).
- Clinical chemistry (including alkaline phosphatase (AP) and blood glucose (BG)) and hematology at study baseline, final visit of the main period V6 (Week 16), and end-of-study visit V18 (Week 64).
- Occurrence of antibodies against BoNT-A in subjects with  $\geq$  30 kg body weight.
- The number of subjects with suicidal ideation, suicidal behavior, and self-injurious behavior without suicidal intent during treatment based on the Columbia-Suicide Severity Rating Scale (C-SSRS).

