#### Adverse Events

AEs will be coded according to the Medical Dictionary for Regulatory Activities (MedDRA) (version in effect when the database is closed).

TEAEs of MP are defined as AEs with onset or worsening after the first injection of NT 201 or Placebo up to and before first injection of the extension period or - in case of discontinuation before second injection – up to and including 16 weeks after first injection of NT 201 or Placebo or date of last study visit, whichever is later. AEs starting in the MP and not having resolved at the final visit of MP (V6) will be followed and further documented in the extension period.

TEAEs of OLEX are defined as AEs with onset or worsening after the first injection of OLEX up to and including 16 weeks after last injection or the date of last study visit, whichever is later.

A detailed description of the rules to be used for the classification of TEAEs can be found in Appendix 1. If an AE worsens between start and end of this AE it will be considered as new AE starting with the date of the worsening. In this case the imputation of end dates within episodes of the same AE will be done by setting the end date/end time to start date/start time of the consecutive worsening record.

In detail missing or partially missing start and stop dates of an AE will be imputed as follows for the calculation of the duration of an AE:

Page 26 of 46

- if start time is missing and date is given and not equal to first exposure date in MP or OLEX, set time to 00:00, else if date is equal to first exposure date in MP or OLEX set time to time of first exposure in MP or OLEX, if given (else 00:00), respectively
- if start time is missing and date is given and equal to the subsequent exposure date in OLEX (e.g. 2nd injection in OLEX), set time to time of the subsequent exposure, if given (else 00:00)
- if start date/time is completely missing and end date is not after or equal to first exposure of MP: no imputation.
- if start date/time is (partially) missing and end date is after or equal first exposure in MP or missing:
  - $\circ$  only start day is missing, but month and year same as first exposure in MP or OLEX: set day and time to day and time of first exposure, else set day to 1 and time to 00:00
  - Start day and month are missing, but year is the same as year of first exposure in the MP (which is ≠ year of first exposure in OLEX): set day, month, time to day, month, time of first exposure in the MP

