Listings will be created for subjects who died, subjects with TEAEs of standard MedDRA query suicide/self-injury and for subjects with possibly suicidal events.

TEAEs for the  $2^{nd}$  injection cycle are defined as adverse events with onset or worsening at or after date of  $2^{nd}$  injection and before date of  $3^{rd}$  injection. TEAEs for the  $3^{rd}$  injection cycle are defined as adverse events with onset or worsening at or after date of  $3^{rd}$  injection and before date of  $4^{th}$  injection. TEAEs for the  $4^{th}$  injection cycle are defined as TEAEs with onset or worsening at or after 4th injection.

Duration of AEs will be listed only. Imputed values will be flagged as such.

In case of missing intensity or missing causal relationship of an AE the worst case principle will be applied, i.e. a missing intensity will be set to "severe" and a missing causal relationship will be set to "related". Missing data of the worst outcome will be imputed by "unknown". If a subject has more than one outcome within a preferred term (PT) only the worst outcome will be used in the frequency tables. Also on subject level only the worst outcome is defined in the following order:

- recovered/resolved
- recovered/resolved with sequelae
- recovering/resolving
- not recovered/not resolved
- unknown
- fatal.

For any missing data on seriousness a worst case strategy will be applied for all analysis tables. The AE will be regarded as 'serious'.

TEAESIs are defined as adverse events occurring after treatment that are thought to possibly indicate toxin spread. The list of adverse events of special interest possibly indicating toxin spread based on MedDRA version 22.0 (version in effect at database closure) is given in Table 4.

MedDRA Preferred Term (MedDRA version 22.0)		
Accommodation disorder	IIIrd nerve paresis	
Areflexia	Ileus paralytic	
Aspiration	IVth nerve paresis	
Botulism	Monoparesis	
Bradycardia	Muscular weakness	
Bulbar palsy	Paralysis	
Constipation	Paraparesis	
Cranial nerve palsies multiple	Paresis	
Cranial nerve paralysis	Paresis cranial nerve	
Diaphragmatic paralysis	Peripheral nerve palsy	
Diplopia	Peripheral paralysis	
Dry mouth: only when severe, serious, or outcome is not recovered, fatal or unknown	Pelvic floor muscle weakness	
Dysarthria	Pneumonia aspiration	
Dysphagia	Pupillary reflex impaired	
Dysphonia	Quadriparesis	
Dyspnoea	Respiratory arrest	
Extraocular muscle paresis	Respiratory depression	

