#### C-SSRS

The number of subjects with suicidal ideation, suicidal behavior, and self-injurious behavior without suicidal intent during treatment based on the C-SSRS will be calculated and presented as proposed in the Columbia–Suicide Severity Rating Scale Scoring and Data Analysis Guide Version 2.0 (Finalized February 2013)[Mary E. Nilsson 2013].

Questions which were documented between one day after start of MP and up to start of OLEX will be assigned to MP. For subjects who discontinued during MP, all questions which were documented at least one day after start of MP will be assigned to MP. Questions which were documented at least one day after start of OLEX will be assigned to OLEX.

The following outcomes are C-SSRS categories and have binary responses (yes/no).

Category 1 – Wish to be Dead

Category 2 – Non-specific Active Suicidal Thoughts

Category 3 – Active Suicidal Ideation with Any Methods (Not Plan) without Intent to Act

Category 4 – Active Suicidal Ideation with Some Intent to Act, without Specific Plan

Category 5 - Active Suicidal Ideation with Specific Plan and Intent

Category 6 – Preparatory Acts or Behavior

Category 7 – Aborted Attempt Category 8 – Interrupted Attempt Category 9 – Actual Attempt (non-fatal) Category 10 – Completed Suicide

The following composite endpoints will be calculated:

- 1. Suicidal ideation (MP): A "yes" answer during MP to any one of the five suicidal ideation questions (categories 1-5) on the C-SSRS.
- 2. Suicidal behavior (MP): A "yes" answer during MP to any one of the five suicidal behavior questions (categories 6-10) on the C-SSRS.
- 3. Suicidal ideation or behavior (MP): A "yes" answer during MP to any one of the ten suicidal ideation and behavior questions (categories 1-10) on the C-SSRS.
- 4. Suicidal ideation (OLEX): A "yes" answer during OLEX to any one of the five suicidal ideation questions (Categories 1-5) on the C-SSRS.
- 5. Suicidal behavior (OLEX): A "yes" answer during OLEX to any one of the five suicidal behavior questions (Categories 6-10) on the C-SSRS.
- 6. Suicidal ideation or behavior (OLEX): A "yes" answer during OLEX to any one of the ten suicidal ideation and behavior questions (Categories 1-10) on the C-SSRS.

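### The SAP's period and cycle definitions of TEAEs use different boundaries on injection days, so adverse events dated on those days are counted inconsistently

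*SAP*

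**What the plan says.** **Periods.** SAP 7.5 (Adverse Events) counts an event in the main period if its onset or worsening falls after the first injection and "up to and before first injection of the extension period". The extension starts where that ends: "TEAEs of OLEX are defined as AEs with onset or worsening after the first injection of OLEX". Both limits are the injection, not its calendar day.

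**Cycles.** Later in the same section, TEAEs for the second "injection cycle are defined as adverse events with onset or worsening at or after date of" the second injection, and end before the date of the third. Cycle 3 follows the same pattern between the third and fourth injection dates. For cycle 4 the word for date is missing: TEAEs for the fourth "injection cycle are defined as TEAEs with onset or worsening at or after" the fourth injection.

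**Missing onset times.** An AE with a date but no start time, dated on the day of the first extension injection, is given the injection time as its start. The SAP introduces these rules as serving the calculation of AE duration and refers to Appendix 1 for detailed TEAE classification. A special rule places an AE in the earliest cycle it could belong to, but only when the doubt is between extension cycles.

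**Visits.** Protocol 7.4 notes that "the pairs of visits 6/6a, 10/10a and 14/14a will normally take place on the same respective day", and the opening of SAP 7 says much the same. Protocol 10.7 schedules dental examinations "at screening (V1), V3 and V6 of the main study period" and requires any worsening to be recorded as an AE. Protocol Table 5 has safety laboratory samples at screening, V6 and V18 only.

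**Other safety data on the same day.** For the C-SSRS the SAP says "Questions which were documented between one day after start of MP and up to start of OLEX will be assigned to MP", and its listing rule counts V6 in the main period. V6 laboratory values are tabulated as the final main-period visit.

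**The concern.** TEAE occurrence, overall and by injection cycle, is the primary safety variable, and SAP 6.5 extends this to overall, per period and by cycle. These tables should reconcile: each AE should belong to one period and to one cycle within it. Two different boundaries on the day when visits normally coincide prevent that.

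The main-period table is also the only randomized safety comparison. V6 supplies its only scheduled post-injection laboratory sample and its last dental examination. If a finding made at V6 before the second injection is dated that day and then treated as starting at that injection, it drops out of the comparison. For a child on placebo it is then displayed as an event under NT 201, although no NT 201 had been given when it was found.

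**Working it through.** The plan states no figure for this point, so the check applies its rules to an AE whose onset date is an injection date, with both visits that day.

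**Step 1. Second injection (V6/V6a).**

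| Onset on that day | Period rule | Cycle rule |
|---|---|---|
| Timed before the injection | Main period, not extension | Cycle 2 |
| Timed after the injection | Extension | Cycle 2 |
| Untimed, imputation used for assignment (onset = injection time) | Not main period, since it is not before the injection; extension only if a tie counts as after | Cycle 2 |
| Untimed, imputation used for duration only | No rule in the SAP text decides | Cycle 2 |

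In the first row cycle 2 holds an event that the extension total excludes. As the main period is the first cycle (SAP 3.1), the event belongs to cycles 1 and 2 at once.

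**Step 2. Third and fourth injections.** An AE timed before the third injection that day is an extension TEAE and falls in cycle 3, though it preceded that cycle's injection. An AE timed before the fourth injection that day is an extension TEAE, but it is not before the date of the fourth injection (so not cycle 3) and not at or after the fourth injection (so not cycle 4). It is in the extension total and in no cycle.

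**Step 3. Would onset times be missing?** Protocol 10.1 lists the date of onset without a time, but the date of resolution with time if applicable. The SAP handles start time as a field that may be present or missing. Some untimed onsets are therefore plausible; how many cannot be known from the documents.

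**Step 4. Does the imputation govern assignment?** The text does not settle this.
- For duration only: that is the stated purpose, and classification is referred to Appendix 1.
- For assignment: duration is stop date minus onset date plus 1, in days, so a clock time added to a known date cannot change it. The special rule for extension cycles also links imputed times to cycle placement, and it allows an untimed AE on an injection date to belong to the previous cycle. The date wording of cycles 2 and 3 rules that out.

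**Step 5. Size.** Planned main-period arms for ages 6–17 are 146 on NT 201 and 73 on placebo (Protocol 12.1). For one subject whose only main-period TEAE moves:
- placebo: 1/73 = 1.4 percentage points;
- NT 201: 1/146 = 0.7 percentage points.

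The share of such subjects is not in the documents. Purely as an assumed range:

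| Assumed share | Placebo (× 73) | NT 201 (× 146) |
|---|---|---|
| 1% | 0.7 | 1.5 |
| 5% | 3.7 | 7.3 |
| 10% | 7.3 | 14.6 |

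With equal shares both incidences fall by the same number of points and the difference is unchanged. With unequal shares it moves in a direction that the documents do not allow one to predict.

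**The case against.** The strongest reply is that the cycle wording does not touch the randomized comparison. That table is the main-period analysis, governed by the period rule, and the period rule keeps an AE timed before the second injection in the main period. This stands. A reader might infer from the date wording that all V6 findings leave the placebo comparison, or that every laboratory-detected AE at V6 is lost. The documents support neither.

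Loss from the main period needs four things together: an onset dated exactly that day, V6 and V6a on the same day, no onset time, and an imputation that decides assignment. A complaint elicited at V6 but dated earlier stays in the main period under both rules. Some children with oral or dental findings may be postponed under the head-and-neck infection criterion in Protocol 7.4, and their AE then predates the injection date. Appendix 1 may state the assignment rule. All of this stands, and it limits the second part of the point to a conditional one.

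It is also fair that both arms follow the same rule, that safety analyses are descriptive, that V6 laboratory values remain visible by treatment in the shift tables, and that attributing an untimed same-day event to NT 201 is cautious for the extension profile. The C-SSRS rule agrees with the main-period boundary; it differs only from the cycle wording and the untimed imputation.

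The reply does not remove the conflict within the SAP text. Whatever Appendix 1 says, two sets of boundaries in one section give different answers on injection days, and the cycle definitions also differ among themselves.

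**Conclusion.** The point holds in two parts.

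**Unconditional.** The boundaries conflict. Followed literally, they count an AE timed before the second injection that day in the main period and in cycle 2 but not in the extension, and leave one timed before the fourth injection that day out of every cycle. By-cycle counts of the primary safety variable will not reconcile with period counts wherever such AEs occur, and a finding made before the injection can be shown as an NT 201 cycle 2 event. This is an error in the stated rules, not a missing detail.

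**Conditional.** If the time imputation also decides the period, untimed AEs first found at V6 before the injection and dated that day leave the main-period table in both arms. The size is 1.4 points of incidence per affected placebo subject and 0.7 per affected NT 201 subject, assuming planned arm sizes and that the AE was the subject's only main-period TEAE. No total and no direction of bias can be given.

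**What to change.** In SAP 7.5:

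1. Use the date and time of injection as the single boundary for both periods and all cycles, with the same treatment of ties throughout.
2. Assign an AE first found at an end-of-cycle assessment made before the injection on an injection day (laboratory, dental, physical examination, vital signs, AE questioning) to the ending period and cycle, unless its onset is documented after the injection. Other untimed AEs dated on the day of V6a stay in the new cycle, which keeps attribution to NT 201 cautious.
3. State that this rule overrides the start-time imputation for assignment at V6/V6a. Between extension cycles the existing rule already sends unclear AEs to the earliest cycle they could belong to; the corrected boundary lets it work as written.
4. Bring Appendix 1 into line.

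This also puts AEs on the same footing as the C-SSRS and the V6 laboratory values.

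The cost is SAP wording and minor programming. The SAP is dated June 2019, at the planned end of the study, so collecting onset times afresh from sites would be burdensome. Existing visit and assessment data can show which AEs arose from a pre-injection assessment, with a query only where the source is unclear. A few such queries are the main downside.

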### 10.1.3 Categories of actions taken and outcome

Action taken with the IP:

- Drug withdrawn (no further study injections given).
- Dose reduced (at the next injection possible i.e. at V10a [injection cycle 3] or V14a [injection cycle 4] only, due to weight loss or AEs).
- Dose increased (at next injection visit i.e. at V10a or V14a only, according to weight gain of subject).
- Dose not changed.
- Unknown.
- Not applicable.
- Drug withdrawn temporarily (further study injections delayed).

The reportable outcomes and/or sequelae of an AE are as follows:

- Recovered/resolved.
- Recovering/resolving.
- Not recovered / not resolved.
- Recovered / resolved with sequelae.
- Fatal.
- Unknown.

If there is more than one AE, only the AE leading to death will be attributed with a "fatal" outcome.

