### Table 7: List of AESIs

In addition to the terms listed in Table 7, adverse event 'dry mouth' considered to be severe, serious or irreversible are also to be reported as AESIs.

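### The SAP ranks *recovered with sequelae* as milder than *recovering* and omits it from the dry-mouth AESI rule, so a small class of events with residual effects is left out of one descriptive table and of the TEAESI count

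*SAP*

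**What the plan says.** SAP section 7.5 (Adverse Events) reduces multiple records to one: "If a subject has more than one outcome within a preferred term (PT) only the worst outcome will be used in the frequency tables". It then adds: "Also on subject level only the worst outcome is defined in the following order". The list that follows is recovered, recovered with sequelae, recovering, not recovered, unknown, fatal. The direction is not stated, but with fatal last it can only run from best to worst. SAP section 6.5.3 plans the worst-outcome tabulation by period and by injection cycle, as one of the other safety variables.

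Protocol section 10.1.3 includes "Recovered / resolved with sequelae" among its six reportable outcomes and gives no ranking.

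For dry mouth, protocol section 10.3 (below Table 7) says that "adverse event 'dry mouth' considered to be severe, serious or irreversible are also to be reported as AESIs". SAP Table 4 implements this as "Dry mouth: only when severe, serious, or outcome is not recovered, fatal or unknown". TEAESI occurrence is a secondary safety variable (protocol 12.3.5.2, SAP 6.5.2). SAP section 8 declares the worst-outcome tabulation as an addition, but mentions neither the ranking nor the mapping of irreversible to outcome codes.

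**The concern.** A worst-outcome table should put an event that left a residual effect above one that is still improving. The SAP does the reverse. Where both outcomes occur in the same subject, the table keeps the one without a recorded residual.

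The dry-mouth rule has a related gap. The only reportable outcome that records a residual effect by name is absent from the list that stands in for irreversible, while *unknown*, which records nothing, is included. Increased dryness of the mouth is among the risks that protocol section 4.3 identifies, and section 4.2 says that absence of long-term dental and oral harm has not been demonstrated. Investigators report irreversible dry mouth as an AESI under protocol section 10.3, so the SAP's count could also disagree with the AESI report forms.

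**Working it through.** There is no planned figure to reproduce. The check enumerates what each rule does. All counts below are combinations of codes, not expected numbers of subjects.

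**Outcome ranking.** Inputs: the six outcomes in the SAP's order, and the rule that the highest-ranked one present is shown.

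- *With sequelae* can be paired with 5 other outcomes. Under the SAP order it is the one shown in 1 of 5 (against *recovered* only).
- It belongs to 2^5 = 32 possible sets of outcomes. It is the worst member only when nothing except *recovered* accompanies it: 2^1 = 2 of 32.
- If *with sequelae* and *recovering* swap places, it is shown in 2 of 5 pairs and 2^2 = 4 of 32 sets.
- The only pair whose result changes is {*with sequelae*, *recovering*}. In sets, 4 − 2 = 2 change: that pair alone, and that pair plus *recovered*.

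So the ranking matters only for subjects whose worst two outcomes are exactly these two. That can arise within a preferred term, since "If an AE worsens between start and end of this AE it will be considered as new AE starting with the date of the worsening", and at subject level across different terms. In a by-cycle table both records must fall in the same cycle. In the extension-period table, which pools three cycles, they need not.

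**Dry-mouth rule.** Inputs: three intensities, serious yes or no, and outcome *with sequelae*, giving 3 × 2 = 6 cells. Under Table 4 a cell counts if the event is severe, serious, or has a listed outcome; *with sequelae* is not listed.

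| Intensity | Non-serious | Serious |
|---|---|---|
| Mild | not counted | counted |
| Moderate | not counted | counted |
| Severe | counted | counted |

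Two of 6 cells are missed. With outcome *unknown*, the same two cells are counted, because *unknown* is listed. If *with sequelae* is added to the rule, 0 of 6 are missed.

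**The case against.** Several points on the other side stand.

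- A lone *with sequelae* event is still shown. Any worst-of scale hides what lies below its top category; the swap leaves sequelae hidden behind *not recovered*, *unknown* and *fatal*.
- Sequelae that amount to lasting or substantial disability make the event serious under protocol section 10.2. They enter the serious-TEAE tables and listings, and for dry mouth they satisfy the AESI rule through its serious arm.
- The documents do not define irreversible. One can argue that dry mouth resolved with sequelae has itself resolved, and that irreversible means *not recovered*, which Table 4 includes. Dental or oral worsening is also recorded as its own adverse event (protocol 10.7). This is why the reading used here is an assumption.
- Safety analyses are descriptive, and specifying outcome codes is the kind of detail an SAP exists to supply. The silence of section 8 is therefore not a serious fault in itself.

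A reader might infer more than the documents support:

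- *Every subject with several differing outcomes is misclassified.* The enumeration shows that one pair changes.
- *A dysphagia that left sequelae vanishes from the safety report.* Dysphagia is an AESI whatever its outcome and is counted and listed as such; only one row of one table is affected.
- *Ranking unknown above not recovered is an error.* It fits the SAP's treatment of missing intensity, causality and seriousness, each set to the worst case. The displaced event moves to a row the SAP treats as worse.
- *A blank outcome makes a mild dry mouth an AESI.* The SAP imputes a missing worst outcome as *unknown*, but does not say whether that imputation feeds the AESI rule.

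**Conclusion.** The point holds in two narrow parts. First, the outcome order puts *with sequelae* on the wrong side of *recovering*, and the sequelae drop out of the worst-outcome table for subjects whose worst two outcomes in that period or cycle are that pair. Second, mild or moderate non-serious dry mouth ending with sequelae is left out of the TEAESI count while the same event with outcome *unknown* is included. In both parts sequelae can only be under-shown.

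The effect is likely small. The documents contain no event counts, so no number can be given. The first part rests on reading the list from best to worst, the only sensible direction. The second rests on reading irreversible to include sequelae, which is reasonable but not stated. Efficacy and the confirmatory tests are untouched. The documents do not support the broader claim that lasting harm is concealed from the safety analysis.

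**What to change.** 1. State in SAP section 7.5 that the outcome order runs from best to worst, and place *recovered/resolved with sequelae* worse than *recovering/resolving*. Leave *unknown* above *not recovered*.
2. Add *recovered/resolved with sequelae* to the dry-mouth rule in Table 4. Keep *unknown* in the rule, since removing it would lower the AESI count and abandon the worst-case approach. Flag events that qualify only through an unknown or missing outcome.
3. State in the SAP how irreversible is mapped to outcome codes, including whether an imputed *unknown* feeds the AESI rule.

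The cost is one changed format, one added condition and a flag in the adverse-event program, and a few lines of text. The downside is that a few events move between rows and the AESI count may rise slightly.
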